The Fondazione IRCCS Ca' GrandaOspedale Maggiore Policlinico is the main public clinical research institute in Italy and has taken a leading role in the medical management of the COVID-19 epidemics in Milan and the Lombardy region. Due to the high volume of patients treated, the ongoing characterization of a large cohort of individuals who acquired the infection without developing symptoms (CoDS study), and scientific leadership in the field of human genetics, the Foundation is in a unique position to conduct a genomewide association study for the identification of the inherited determinants of the susceptibility to severe COVID-19.

Hypothesis

Host genetic factors contribute to development of severe pulmonary disease in patients with SARS-CoV-2 infection.

Purpose and aims

The purpose of the entire project is to identify genetic determinants of the predisposition to develop respiratory failure in persons infected by SARS-CoV-2; knowledge of these factors may educate the biological understanding of the development of severe lung disease in SARS-CoV-2 infection. Such an understanding may inform treatment trials of potential utility towards more effective management of this patient group. A polygenic risk score may also be useful in identifying high/low risk patients, eg among health-care providers and vulnerable individuals with significant comorbidities.

Specific aims of the project are:

1. To identify the main common genetic determinants of severe COVID-19 by conducting a GWAS:
in first phase we will compare the first 1,000 cases (SARS-CoV-2 positive patients with severe lung affection) to 5,000 historical healthy controls from the same geographic area, in order to provide initial data informing the research in the field in a timely fashion. This will be conducted in close collaboration with the University of Kiel COVID-19 genomic initiative. Later on, we will proceed to assess objectives 1 and 2 in the full cohort, including also infected controls who did not developed clinically significant symptoms.

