1) To identify differences in genetic background between patients with severe SARS-CoV-2 infection and healthy controls from the same geographic area

ENDPOINTS: SNPs as identified by GWAS

2) To identify differences in genetic background between patients with severe versus mild or moderate SARS-CoV-2 infection

ENDPOINTS: SNPs as identified by GWAS

Study Design

Cross-sectional study, with non-standard study-specific biological testing.

The study consists of two phases as reported in the project timeline:

1. In the first phase of the study, we will compare the first 1,000 cases (SARS-CoV-2 positive patients with severe lung affection) to 5,000 historical healthy controls from the same geographic area, in order to provide initial data informing the research in the field in a timely fashion. This will be conducted in close collaboration with the University of Kiel COVID-19 genomic initiative.
2. In the second phase of the study, we will proceed to analyze the full cohort, including also infected controls who did not develop clinically significant symptoms.

Participants (eligibility)

1. Cohort 1: Cases

SARS-CoV-2 positive patients (no age limit) with severe lung affection defined by hospitalization and respiratory failure requiring support of any kind (ranging from O₂support via non-invasive ventilation to full respirator/ECMO) at the Fondazione IRCCS Ca' Granda. These patients will be selected among those enrolled in the "COVID-19 Network", "EPIDEMIOLOGICAL AND CLINICAL CHARACTERISTICS OF PATIENTS HOSPITALIZED IN ITALIAN INTENSIVE THERAPY AFFECTED BY 2019-NCOV: COHORT STUDY MULTI-CENTRIC RETROSPECTIVE-PROSPECTIVE: 2019-nCoV_ICU", and other COVID-19 research registries sponsored by the IRCCS Ca' Granda Foundation.

- Informed consent

2. Cohort 2: Mild/moderate infection controls

- blood donors (age 18-70 years) donating between 24/02/2020 and 18/05/2020 (~7,500 donors) which will be confirmed to have been infected with SARS-CoV-2 without developing clinically significant symptoms, identified in the CoDS project "COVID-19 Donor Study" sponsored by the Foundation
- confirmed to be exposed to the virus (by means of positive viremia and/or IgM/G antibodies).
- informed consent

3. Cohort 3: Healthy controls (general population controls)

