Substudy: to examine the possible role of rare genetic variants in determining the predisposition to severe COVID-19, DNA (isolated from the same biological samples of the main study) of individuals who developed severe respiratory failure requiring ventilation despite age < 50 years and lack of comorbidities and risk factors will be further sequenced and analyzed by Whole exome sequencing (WES) at the Department of Molecular Medicine of the University of Kiel ([name]).

Any leftover of biological samples will be stored at Biobank POLI-MI for additional 15 years under the responsibility of [name].

Potential biases and pitfalls

Samples of insufficient quality due to low call rate (<0.95%) or outlying heterozygosity will be excluded. To set of LD-pruned SNPs with MAF>40% were used to estimate identity by descent (IBD) and ancestry and any closely related individuals excluded. Principal component analysis will be used to exclude samples with non-European ancestry. SNPs with a minor allele frequency less than 0.1%, Hardy-Weinberg equilibrium P < 10⁻⁷, call rate lower than 95% will be excluded as well.

In order to be able to compare data to other cohorts to increase the sample power and allow replication, we will proceed to single nucleotide polymorphisms (SNP) imputation in the cases was carried out using the Michigan Imputation Server (<https://imputationserver.sph.umich.edu/start.html#!pages/home>). Each cohort was uploaded to the Michigan Imputation Server and imputed to the Haplotype Reference Consortium (HRC 1.1r 2016) reference panel. Imputed genotypes will be filtered by an r₂score of at least 0.8, and only overlapping well-imputed SNPs between the two cohorts will be retained.

Department of Services and Preventive Medicine UOC
Transfusion Center [contact]

- Director: [name]

In case during the planned analyzes we will need a larger sample size to answer the research questions, we will actively involve cases from collaborating hospitals and the international collaborative network.

Study variables and data sources

A biorepository (serum samples and buffy coats for DNA extraction) is being established and maintained within the Fondazione IRCCS PoliclinicoPOLI-MI Biobank (at the coordinating Unit).

Cohort 1: Cases

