Extensive clinical data with prospective follow-up and samples of these individuals are already being collected within the "Register for the evaluation of epidemiological characteristics and patient clinics hospitalized at the COVID-19 units: COVID-19 network" and "characteristics epidemiological and clinical findings of patients hospitalized in Italian intensive care units affected by 2019-nCoV: multicenter retrospective-prospective cohort study: 2019-nCoV-ICU". We will also involve collaborating centers in Lombardy and Northern Italy.

Cohort 2: mild/moderate infections controls

All donors undergo clinical evaluation, including updating of medical history, and biochemical testing at each blood donation. For each blood donation, the possible development of flu-like symptoms in the two weeks following blood donation will be recorded as well. All donors are indeed asked to report the development of any symptom potentially related to COVID-19 in the 14 days after the procedure, by contacting a dedicated phone number, and all calls are managed by medical personnel of the Transfusion center. All these events, as well as all the other data that will be collected for this study, are registered in the EMONET 15 informatics system.

Cohort 3: healthy controls

> 5,000 historical healthy controls from the same geographic area (data derived from previous studies conducted at other institutions), in order to provide initial data informing the research in the field in a timely fashion. This will be conducted in close collaboration with the University of Kiel and Oslo COVID-19

genomic initiative, which includes collaborators from the Milan area (San Gerardo and Humanitas Hospitals).

Statistical issues

Sample size

Group	Sample size	Source/notes
Cases	2000	Ca' Granda ICU and medicine departments
Mild/moderate controls	2000	based on an estimated cumulative prevalence of SARS-CoV-2 infection >10% in Lombardy at the time of project writing, we estimate to enroll at least 1,000 controls for the study (blood donors).
Healthy controls	5000 (including collaborating centres)	Historic data

The study is originally scoped toward 2,000 cases, but if more samples are collected, the experiment will be expanded (for which there is both capacity and funding).

The study is a case-control cross-sectional study. Two main comparisons will be performed:

- 1) cases vs healthy controls (phase 1)
- 2) cases vs mild/moderate infections (phase 2)

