In the hypothesis that we will recruit 2,000 cases and consider 5,000 controls, we will have >99% power to detect a 4-fold increase in the risk of severe COVID-19 for variants that have a minor allele frequency >30% in the population (two sided, for a significance threshold of P values $< 10^{-8}$ generally employed in GWAS), and a good power (>80%) to detect an impact of rarer variants or of variant with smaller size effects.

Associations with very weak effect sizes may be missed with the crude approach, but for this study this compromise is acceptable to achieve feasibility and speed.

Statistical analysis plan

Statistical association analysis will be performed using logistic regression / linear mixed models, based association methods with standard tools (eg SAIGE, BOLT-LMM, PLINK etc.) and appropriate correction for population stratification confounders, and incorporating patient age and gender as co-variables. For strong genetic signals (egHLAin many immune mediated diseases, IL28B in HCV infection, complement factor H polymorphisms in age-related macular degeneration) only a few hundred patients have been required to achieve genome-wide significant findings.

The comparison will be carried out on imputed genotypes, firstly from the set obtained from imputing both cases and controls together, and then again from the set obtained by imputing all cohorts separately and then combining stringently filtered genotypes. LocusZoom plots will be examined for visualization of the signal around significantly associated SNPs.

For each trait the analysis will be performed with no clinical covariates and then again with the following additional covariates: presence of arterial hypertension, diabetes, chronic obstructive pulmonary disease, type of respiratory support.

Ethical considerations

Regulatory standards

This study will be conducted by Good Clinical Practice (GCP) rules; in accordance with the ethical principles that have their origin in the Declaration of Helsinki and with the respect to the European clinical practice, in compliance with all international guidelines and national law regulation in Italy.

Institutional review board / independent ethics committee

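### The planned 2,000 infected controls are not supported by the one named donor pool at the stated prevalence, and objective 2 has no power figure

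*Combined protocol and SAP*

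**What the plan says.** In the Sample size table (Statistical issues), the size column gives 2,000 for mild/moderate controls. The note in that row cites a cumulative prevalence above 10% in Lombardy when the project was written and continues: "we estimate to enroll at least 1,000 controls for the study (blood donors".

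Cohort 2 is defined under Participants (eligibility). It consists of blood donors from the COVID-19 Donor Study, "donating between 24/02/2020 and 18/05/2020 (~7,500 donors", who must be "confirmed to have been infected with SARS-CoV-2 without developing clinically significant symptoms" and must give informed consent. No other source of infected controls is named.

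Three passages speak of enlarging the study.

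- Potential biases and pitfalls: "we will actively involve cases from collaborating hospitals and the international collaborative network".
- Study variables and data sources, under Cohort 1 (cases): "We will also involve collaborating centers in Lombardy and Northern Italy". The table also mentions collaborating centres in the healthy-control row.
- Below the Sample size table, a sentence allows expansion if more samples are collected. It opens from the target of 2,000 cases.

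Two main comparisons are listed: cases versus healthy controls and cases versus mild/moderate infections. There is one power statement: "In the hypothesis that we will recruit 2,000 cases and consider 5,000 controls, we will have >99% power to detect a 4-fold increase", for a minor allele frequency (MAF) above 30% and a two-sided threshold of 1e-8. It goes on to claim "a good power (>80%) to detect an impact of rarer variants or of variant with smaller size effects". The next sentence accepts that very weak effects may be missed.

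**The concern.** One table row carries two sizes for cohort 2, and neither follows from the stated prevalence and the stated donor pool. A prevalence given only as a lower bound can support only a lower bound on the yield, and that bound is below both numbers.

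Objective 2 is one of the two main comparisons, and cohort 2 is its limiting group. The only power figure uses the healthy-control number, so it belongs to objective 1. More exactly, it fits the later analysis announced under Purpose and aims ("we will proceed to assess objectives 1 and 2 in the full cohort"), because the initial phase 1 comparison has 1,000 cases. The clause claiming more than 80% power gives neither an effect size nor an allele frequency. A reader therefore cannot tell which effects a null result in objective 2 would exclude.

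**Working it through.** **Inputs from the documents.** Donor pool about 7,500 (Participants, cohort 2). Prevalence above 10%, cohort 2 size 2,000 with at least 1,000 in the note, 2,000 cases, and 5,000 healthy controls (Sample size table). Initial phase 1: 1,000 cases versus 5,000 controls (Study Design). Two-sided alpha 1e-8, 4-fold effect, MAF 30% (power statement).

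**Yield of the donor pool**

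- At the 10% floor: 7,500 × 0.10 = 750. At 15%: 1,125. At 20%: 1,500.
- Prevalence needed for 1,000: 1,000 / 7,500 = 13.3%.
- Prevalence needed for 2,000: 2,000 / 7,500 = 26.7%.

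These figures are before the symptom restriction, consent and genotype quality control. The documents give no rate for those losses. Assume 80% remain, with a range of 60% to 100%:

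- At 10% prevalence: 750 × 0.8 = 600 (range 450 to 750).
- For 1,000: 13.3% / 0.8 = 16.7% (range 13.3% to 22.2%).
- For 2,000: 26.7% / 0.8 = 33.3% (range 26.7% to 44.4%).

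**Power method.** Allelic two-proportion test on 2n alleles per group. With control allele frequency p and per-allele odds ratio OR, the case frequency is q = p·OR / (1 − p + p·OR). Power is Φ[(q − p − z·SE0) / SE1]. SE0 uses the pooled frequency, SE1 the separate frequencies, and z = 5.73 for two-sided alpha 1e-8. The calculation is unadjusted for covariates.

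**The plan's own figure.** For 2,000 versus 5,000, OR 4 and p = 0.30, q = 1.2 / 1.9 = 0.632 and power is about 100%. The claim of more than 99% reproduces. At the same effect, power is also about 100% for 1,000 versus 5,000 and for 2,000 cases versus 2,000, 1,000 or 750 infected controls. The claim therefore does not distinguish the designs.

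**One case in full.** For 2,000 versus 750, OR 1.5 and p = 0.30:

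- q = 0.45 / 1.15 = 0.3913, so q − p = 0.0913.
- Pooled frequency = (4,000 × 0.3913 + 1,500 × 0.30) / 5,500 = 0.3664.
- SE0 = 0.01459 and SE1 = 0.01413.
- (0.0913 − 5.731 × 0.01459) / 0.01413 = 0.545, so power is 71%.

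**All designs.** Odds ratios below 4 are illustrative; the plan names none.

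| Comparison (cases vs controls) | OR at 80% power, MAF 30% | OR at 80% power, MAF 10% | Power at OR 1.5, MAF 30% |
|---|---|---|---|
| Objective 1, full: 2,000 vs 5,000 | 1.30 | 1.45 | about 100% |
| Objective 1, initial: 1,000 vs 5,000 | 1.40 | 1.60 | 98.6% |
| Objective 2: 2,000 vs 2,000 | 1.37 | 1.57 | 99.8% |
| Objective 2: 2,000 vs 1,000 | 1.47 | 1.74 | 89% |
| Objective 2: 2,000 vs 750 | 1.53 | 1.85 | 71% |

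At OR 1.4 and MAF 30%, objective 2 power is 91%, 50% and 29% with 2,000, 1,000 and 750 infected controls.

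Simulation with 20,000 replicates at the tabulated detectable ORs gave 79% to 82% power for score and Wald tests at both allele frequencies. The likelihood-ratio test gave 79% to 82% at MAF 30% and 75% to 86% at MAF 10%, so the MAF 10% values are approximate.

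**The case against.** **The prevalence is an open lower bound.** 1,000 of 7,500 needs 13.3%, which is compatible with a figure above 10%. The estimate dates from the writing of the project, the donation window runs to 18 May 2020, and cumulative prevalence cannot fall. The row can also be read as a target of 2,000 with a minimum of 1,000. This stands as far as it goes: 1,000 is not ruled out. But the plan states no prevalence that delivers it, does not label the two numbers, and offers nothing near the 26.7% that 2,000 requires.

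**The study can be expanded.** The sentence below the table speaks of samples, and extra cases would raise objective 2 power even with cohort 2 fixed. By the method above, 3,000 cases versus 750 controls gives 80% at OR 1.5 and MAF 30%, against 71% with 2,000 cases. That is correct, but it does not add infected controls. The sentence is scoped to cases and names no further donor source.

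**The consequence for power is modest.** At the plan's 4-fold effect nothing is lost. At OR 2 and MAF 10%, 2,000 versus 750 still gives about 97%, so the clause on more than 80% power is true for some smaller effects. The plan also openly trades sensitivity to very weak effects for speed. This stands and limits the severity. The clause still has no boundary, and the effect that objective 2 can detect depends on which cohort 2 size is reached.

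**The calculations are simplified.** The loss rates are assumed, and the odds ratios come from an unadjusted allelic test, whereas the plan adjusts for age, gender and population stratification. Both points are fair. The 750, 13.3% and 26.7% figures depend on neither.

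**Conclusion.** The concern holds. The planned 2,000 infected controls are not supported by about 7,500 donors at any prevalence the plan states, and the minimum of 1,000 is reached only if prevalence exceeds the stated floor by a third (13.3% against 10%). At the floor the pool gives about 750 before losses, which is 25% below 1,000 and 62.5% below 2,000.

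Objective 2 has no power figure of its own. Across cohort 2 sizes of 2,000, 1,000 and 750, the detectable odds ratio at MAF 30% moves from 1.37 to 1.47 to 1.53. The power statement as written is correct for 2,000 versus 5,000 and is not in question.

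The yield conclusion rests only on the plan's own numbers. The detectable odds ratios assume an additive per-allele effect, an unadjusted test and 2,000 cases. This should be fixed, but it does not threaten detection of a 4-fold effect.

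**What to change.** 1. In the Sample size table, state the prevalence and expected yield, or name the additional donor source, behind the cohort 2 size. If neither can be given, replace the figure with what the pool supports: about 750 at 10%, marked as the yield at the prevalence floor, less expected losses.
2. Say which of 2,000 and 1,000 is the target and which the minimum.
3. Give a detectable odds ratio, with allele frequency, power and alpha, for each comparison as it will be run: 2,000 versus 5,000, the initial 1,000 versus 5,000, and 2,000 versus the expected cohort 2. Say whether the figures are adjusted for covariates.
4. Tie the clause on more than 80% power to those odds ratios and allele frequencies, so that the concession on very weak effects has a boundary.

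The cost is a few lines in the sample size section and less favourable stated figures. No extra participants are needed.

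### The >80% power stated for rarer variants or smaller effects has no frequency or effect-size limit, and 2,000 cases v 5,000 controls do not have it in general

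*Combined protocol and SAP*

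**What the plan says.** The power statement is in the combined protocol and SAP, Statistical issues, Sample size. It starts from stated group sizes: "In the hypothesis that we will recruit 2,000 cases and consider 5,000 controls". For these it says that "we will have >99% power to detect a 4-fold increase in the risk of severe COVID-19". That scenario is limited to MAF above 30%, and the test is specified as "two sided, for a significance threshold of P values $< 10^{-8}$ generally employed in GWAS". The same sentence then adds "a good power (>80%) to detect an impact of rarer variants or of variant with smaller size effects".

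The >99% figure has an effect size, a frequency, a significance level and group sizes. The >80% figure has none of its own except the group sizes and significance level it inherits. Neither comes with a genetic model, nor with a statement whether the fold increase is per allele or per carrier. The next sentence accepts that very weak effects may be missed, in exchange for feasibility and speed. It gives no number.

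Two other places bear on the claim. Potential biases and pitfalls sets the quality-control filter ("SNPs with a minor allele frequency less than 0.1" per cent are excluded) and retains imputed SNPs with r2 of at least 0.8. Statistical analysis plan says that the comparison is run on imputed genotypes.

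**The concern.** A power figure means something only for a given effect and frequency. Here a specific number, more than 80%, is attached to two open-ended classes of variant, and no calculation, table or limit in the document supports it. A reader will naturally take it as a property of the design.

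What is at stake is how an absent signal is understood. The project aims at a genetic risk score and at identifying people at high and low risk. If a locus of moderate effect or low frequency does not reach significance, an unbounded >80% invites the conclusion that it probably has no effect. For many such loci the scan would usually miss a real effect. The lack of a boundary also leaves the provision to add cases without a criterion: the plan does not say which effects 2,000 cases already cover.

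**Working it through.** **Inputs from the sample size section.** 2,000 cases and 5,000 controls, so 4,000 and 10,000 alleles; two-sided alpha 1e-8, so z = 5.731; for the quantified scenario, a 4-fold effect at MAF 30%.

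**Assumptions, because the plan is silent.** The fold increase is a per-allele OR under an additive model; the minor allele increases risk; control frequency equals population MAF; the SNP is perfectly typed.

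**Formulas** (allelic two-proportion test, p0 = control frequency):
- p1 = OR × p0 / (1 + p0 × (OR − 1))
- p̄ = (4,000 p1 + 10,000 p0) / 14,000
- s0 = √[p̄(1 − p̄)(1/4,000 + 1/10,000)]
- s1 = √[p1(1 − p1)/4,000 + p0(1 − p0)/10,000]
- power = Φ[(p1 − p0 − 5.731 × s0) / s1]

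**Step 1: the plan's >99%.** p0 = 0.30 and OR 4 give p1 = 1.2/1.9 = 0.6316, p̄ = 0.3947, s0 = 0.009145, s1 = 0.008898. Then (0.3316 − 0.0524)/0.008898 = 31.4, so power is effectively 100%. Dominant and recessive models also give 1.000. The figure reproduces.

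**Step 2: one moderate effect in full.** p0 = 0.05 and OR 1.5 give p1 = 0.075/1.025 = 0.07317, p̄ = 0.05662, s0 = 0.004324, s1 = 0.004659. Then (0.02317 − 0.02478)/0.004659 = −0.345, and Φ(−0.345) = 37%.

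**Step 3: the same calculation elsewhere.**

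| MAF | OR | Power |
|---|---|---|
| 30% | 1.20 | 13% |
| 30% | 1.25 | 46% |
| 30% | 1.30 | 81% |
| 10% | 1.3 | 12% |
| 10% | 1.5 | 92% |
| 5% | 1.5 | 37% |
| 1% | 2 | 18% |
| 1% | 3 | 98% |
| 0.5% | 4 | 97% |
| 0.3% | 4 | 70% |
| 0.2% | 4 | 35% |

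**Step 4: where 80% is reached.** Solving power = 0.80 for the OR gives the boundary. For imputed SNPs the numbers of cases and controls are multiplied by the lowest r2 retained: 0.8 × 2,000 = 1,600 and 0.8 × 5,000 = 4,000. The last column is for a protective minor allele, perfectly typed.

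| MAF | OR, perfectly typed | OR, imputed at r2 0.8 | Protective OR |
|---|---|---|---|
| 30% | 1.30 | 1.34 | 0.76 |
| 10% | 1.45 | 1.51 | 0.63 |
| 5% | 1.63 | 1.72 | 0.50 |
| 1% | 2.53 | 2.76 | essentially unreachable |
| 0.5% | 3.34 | 3.71 | not reached |

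Holding OR at 4 and solving for frequency, power reaches 80% at MAF of about 0.34%, or 0.43% at r2 0.8. The normal approximation is favourable at very low frequency: a simulated exact conditional test gave 18% instead of 35% at MAF 0.2%, and 96% instead of 97% at MAF 0.5%. The 0.34% is therefore approximate and, if anything, optimistic.

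**The case against.** The best defence is that rarer and smaller are relative to the scenario just given, so the sentence promises good power for some variants beyond it, not for all. On that reading it is true over a wide region: at OR 4, down to a frequency roughly ninety times below 30% (30/0.34 ≈ 88), and at MAF 30%, down to an OR of about 1.30. That stands, and it makes this an unsupported generalisation, not a miscalculation. But read as some variants, the figure carries no information, because any design with near-certain power in one scenario has 80% power slightly beyond it.

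The plan also admits that very weak effects may be missed, and provides for more cases and for collaboration. Both are to its credit. The caveat is not a boundary, though. It does not mention rarer variants, and OR 1.5 at MAF 5% or OR 2 at MAF 1% are not plainly very weak.

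Three stronger readings are tempting and are not supported:
- A reader might take the 0.1% MAF filter as the range over which power is claimed. There a 4-fold effect has about 6% power by the formula above and about 1% by an exact test. But the filter is a quality-control rule, the study is aimed at common variants, and rare variants have their own exome-sequencing substudy.
- A reader might note that about 98 cases with 2.5 controls each already give 99% power in the 4-fold scenario, and infer that 2,000 cases are unjustified. The >99% figure is correct, and the plan presents 2,000 as an expandable scope, not as derived from that scenario.
- A reader might infer that the plan intends to treat a null result as evidence of no effect. No section says so; the risk lies in how the unqualified figure may be used.

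**Conclusion.** The concern holds as a defect in a stated power claim. More than 80% is not a general property of 2,000 v 5,000 at two-sided P<1e-8. For variants of ordinary frequency and moderate effect, power ranges from 12% (OR 1.3, MAF 10%) to 46% (OR 1.25, MAF 30%). The claim is true on one side of a boundary that the plan does not give: OR of about 1.30 at MAF 30%, rising to 2.53 at MAF 1% and 3.34 at MAF 0.5%.

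These sizes rest on an additive per-allele model, a risk-increasing minor allele, control frequency equal to MAF and perfect typing. Two of these assumptions favour the plan: imputation at the lowest retained r2 raises every boundary, and protective minor alleles need stronger effects. The >99% statement is correct and needs no change beyond naming its model. The design itself is not called into question.

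**What to change.** Replace the >80% clause in the sample size section with a bounded statement:

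> Under an additive model with a risk-increasing minor allele, 2,000 cases and 5,000 controls give 80% power at two-sided P<1e-8 for per-allele OR 1.30, 1.45, 1.63, 2.53 and 3.34 at MAF 30%, 10%, 5%, 1% and 0.5% (about 1.34, 1.51, 1.72, 2.76 and 3.71 for SNPs imputed at r2 0.8). A 4-fold effect falls below 80% power under MAF of about 0.34% (0.43% at r2 0.8). Protective minor alleles need stronger effects (OR about 0.76, 0.63 and 0.50 at MAF 30%, 10% and 5%). Absence of a signal outside these limits is not evidence of no effect.

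Name the same genetic model for the 4-fold scenario. If another model is intended, recompute the list under it. The cost is protocol wording only: the stated sensitivity becomes less favourable, and no sample size, procedure or analysis changes.

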Healthy control data of Italian individuals available from previous multi-ethnic assessments (n=5,000, age 14-80 years). These data are already present within a database at the University of Kiel comprising more than 50,000 cases and are available for the analysis of this study.

Department of Services and Preventive Medicine UOC
Transfusion Center [contact]

- Director: [name]

Study flowchart

	Baselines
Timing	04/01/2020 – 09/30/2020
ROUTINE ASSESSMENT:	
Clinical evaluation	X
Medical history ^{to}	X
Clinical outcomes ^b	X
Basic biochemical panel ^b	X
Collection of blood sample for DNA extraction	X

^{to}Including family history, lifestyle evaluation, physical activity, alcohol and smoking, risk factors for communicable disorders, comorbidities.

^bas specified in the research registries in which the patients are enrolled.

Genomic study, laboratory methods

In the first phase of the study, identified peripheral blood samples from severely affected cases (cases, cohort 1) will be sent to the Department of Molecular Medicine of the University of Kiel: [name] will be responsible for storage and analysis of the samples. Genotyping will be performed by Illumina GlobalScreeningArray-24 v3.0 + Multi-Disease array (Illumina), at the Department of Molecular Medicine of the University of Kiel. At the end of the analyses, any leftover of biological samples will be sent back to IRCCS Ca' Granda Foundation.

In the second phase of the study, DNA will be extracted from identified peripheral blood samples from mild/moderate infection controls (cohort 2) at the Genomic platform of the Fondazione IRCCS Ca' Granda.

Deidentified DNA samples will be sequenced at the Fondazione IRCCS Ca' Granda by using the same approach. [name] in collaboration with [name] (Scientific direction) will be responsible for the genomic analyzes of these samples at the Fondazione IRCCS Ca' Granda.

Department of Services and Preventive Medicine UOC
Transfusion Center [contact]

- Director: [name]

The genetic risk profile (common inherited variants) will be evaluated at genomewide level by Illumina Infinium Global screening array (Illumina), and frequency distributions of common genetic variants will be compared between donors who cleared the infection without developing severe symptoms and patients admitted for respiratory failure (enrolled by the COVID-19 research networks of the Fondazione IRCCS Ca' Granda).

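### Type of respiratory support is listed as a covariate without restriction to case-only analyses, although in both case-control comparisons it is part of the case definition

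*Combined protocol and SAP*

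**What the plan says.** The Statistical analysis plan describes two runs. The first is clear: "For each trait the analysis will be performed with no clinical covariates". The second repeats it, "then again with the following additional covariates: presence of arterial hypertension, diabetes, chronic obstructive pulmonary disease, type of respiratory support". The models named are "logistic regression / linear mixed models", with age and gender included. No coding is given for type of support, and nothing says which traits the second run covers.

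Under Participants (eligibility), Cohort 1 is defined by "hospitalization and respiratory failure requiring support of any kind", from oxygen up to full respirator or ECMO. Cohort 2 consists of blood donors confirmed as "infected with SARS-CoV-2 without developing clinically significant symptoms". Cohort 3 is described as "Healthy control data of Italian individuals available from previous multi-ethnic assessments", and under Study variables and data sources as historical.

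The Sample size section names two main comparisons: cases against healthy controls in phase 1, and cases against mild or moderate infections in phase 2. Work within cases appears in secondary aim 2 (outcomes, clinical characteristics and treatment response), which the covariate sentence does not mention.

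**The concern.** A covariate should carry information beyond the outcome. Here every case has some support by definition. Cohort 2 controls have none by definition. Cohort 3 controls have none, or no record of it, by inference from their being healthy and historical. Adjusting a case-control model for support therefore adjusts for the outcome.

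At stake is the only clinically adjusted analysis in the statistical section. Followed literally, it either fails, so that someone must choose after seeing the data whether to drop the term, recode it or abandon the run, or it runs under a coding that changes what is estimated. In the second case, a weakened signal could be misread as one explained by clinical factors.

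**Working it through.** **1. The plan's own figure.** The power statement assumes 2,000 cases, 5,000 controls, minor allele frequency (MAF) 30%, a 4-fold risk and two-sided P < 10⁻⁸. Reading 4-fold as an allelic odds ratio (OR), the case allele frequency is 0.30×4/(0.70+0.30×4) = 1.2/1.9 = 0.632. With 4,000 against 10,000 alleles, power is about 100%, in agreement with the stated >99%. The support covariate plays no part in it.

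**2. Structure.** Let Y = 1 for a case and let S be support level: 0 for none, 1-3 for increasing support (the three levels are an assumption). The cohort definitions give Y = 1 exactly when S > 0, taking Cohort 3 as having no support.

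**3. Logistic model, no support as its own level.** The predictor −c + 2c·1(S>0) classifies everyone correctly for any c > 0, and the likelihood tends to 1 as c grows. The score version −c + 2cS does the same. No finite maximum-likelihood estimate exists, whatever the OR, MAF or split of support types.
- A linear-programming check with age and sex in the model used 1,000 v 5,000, 2,000 v 5,000, 2,000 v 2,000 and 2,000 v 1,000, at OR 1.5 and 4. It found complete separation in 24 of 24 data sets with indicators, 24 of 24 with a 0-3 score and 0 of 24 without the support term.
- In one simulated 2,000 v 5,000 data set (OR 1.5, log-OR 0.405), the SNP log-OR was 0.38 (SE 0.039) without support. With indicators it was −0.000004 (SE 4.9) after 10 iterations and 0.16 (SE 66) after 20, without convergence.

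**4. Linear model with indicators.** Y equals the sum of the three indicators, so the fit is exact and the SNP coefficient is zero. Check: R² = 1.0, coefficient below 10⁻¹⁴.

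**5. Support missing in controls.** Complete-case analysis keeps only cases, and Y no longer varies.

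**6. Codings that run (illustrations only).** Assumed here: MAF 30%, and genotype unrelated to support level within cases.

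(a) *Linear model, 0-3 score.* With m and v the mean and variance of the score in cases, p the case fraction and G genotype, the retained share of the SNP coefficient is v/[m²(1−p)+v], divided by 1 − cov(G,S)²/[var(G)var(S)]. For an assumed split of 60/20/20, m = 1.6, m² = 2.56 and v = 0.64:

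| Cases v controls | p | v/[m²(1−p)+v] | Exact, OR 1.5 | Exact, OR 4 |
|---|---|---|---|---|
| 1,000 v 5,000 | 0.167 | 0.64/2.773 = 0.231 | 0.233 | 0.255 |
| 2,000 v 5,000 | 0.286 | 0.64/2.469 = 0.259 | 0.262 | 0.297 |
| 2,000 v 2,000 | 0.500 | 0.64/1.920 = 0.333 | 0.337 | 0.384 |
| 2,000 v 1,000 | 0.667 | 0.64/1.493 = 0.429 | 0.433 | 0.477 |

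Over splits 80/10/10, 60/20/20, 34/33/33 and 20/40/40, the share is 12-27% (phase 1) and 19-44% (phase 2) for OR 1.2-2.0, and 14-30% and 22-48% at OR 4.

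(b) *Oxygen-only merged with no support, indicators for the two higher levels.* Only oxygen-only cases and controls now inform the SNP effect. Logistic regression gives a finite OR of about 1.49-1.52 for an assumed 1.5, but for oxygen-only cases v controls. In a linear model, with w the oxygen-only share, the retained share is about w(n₁+n₀)/(w·n₁+n₀) for n₁ cases and n₀ controls. With w = 0.6 this is 3,600/5,600 = 0.64, 4,200/6,200 = 0.68, 2,400/3,200 = 0.75 and 1,800/2,200 = 0.82 for the four sizes. Simulation gave 64-83%.

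(c) *Firth-penalised logistic with full indicators.* It converges but is uninformative: SNP −0.12 (SE 0.93) at 2,000 v 5,000.

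**7. After the fix.** With support removed and the three comorbidities kept (at assumed rates), the log-OR was 0.40 (SE 0.041) at 2,000 v 5,000 and 0.43 (SE 0.049) at 2,000 v 2,000, against a true 0.405. Using support to select cases also works: the two higher support levels v controls, without a support term, recovered an OR of 1.5 as 1.48-1.53.

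**The case against.** **Scope.** Speaking of each trait suggests several phenotypes, and secondary aim 2 has several within cases, where support varies and the model is estimable. The sentence may have been meant for those. This stands as a possible intention, so the documents do not show that an invalid case-control analysis was deliberately planned. But nothing limits the sentence to them, and the statistical section names only the two case-control comparisons.

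**Estimability.** A reader might infer that the rerun cannot yield a SNP estimate under any coding, or that only a numeric score would run unnoticed. Step 6(b) refutes both.

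**Size.** A reader might take 12-48% as the bias in this plan. It is not. The coding, splits and ORs are assumed, and so is independence of genotype and support level within cases. With an assumed within-case allelic OR of 1.2 per level, the 60/20/20 shares fall from 23-43% to 5-12% in simulation.

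**Importance.** The rerun is secondary, and separation, an exact fit or the loss of all controls would be noticed. That limits the harm, but the prespecified run still could not be carried out as written.

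**Cohort 3.** Absence of support there is inferred. The documents do not list which clinical variables the historical data hold.

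**Conclusion.** The covariate list is wrong as written for both case-control comparisons and should be corrected. The failures in steps 3 and 4 follow from the cohort definitions once no support is a separate level (for Cohort 3, by inference), and need no assumed effect size. Step 5 applies if support is unrecorded in controls. The codings examined that do run either shrink the effect, restrict it to oxygen-only cases or leave it uninformative. Because the plan specifies no coding, no single size of bias can be attached to it.

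A reader might go further and conclude that the main association results are compromised. The documents do not support that: the run without clinical covariates is separate, and both objectives and the power statement stand without the support term.

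**What to change.** Remove type of respiratory support from the covariates of both case-control comparisons and keep hypertension, diabetes and COPD as listed. Suggested wording: *Type of respiratory support will not be a covariate in case-control models; it may be used only in case-only analyses (secondary aim 2) or to define case subgroups.* For case-only analyses, also state how it is coded and whether it is a covariate or an outcome. This leaves intact the rare-variant substudy, which uses ventilation to select cases.

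The cost is one sentence, with no new data and no extra run. The ethics section requires committee approval of protocol amendments, so there is a small administrative step.
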